9.7 Other Analyses

Not applicable.

9.7.1 Analyses of Pharmacokinetic or Pharmacokinetic/Pharmacodynamic Endpoints

Not applicable.

9.7.2 Analyses of Clinical Outcome Assessments

Not applicable.

9.7.3 Analyses of Health Economic Endpoints

Not applicable.

9.7.4 Analyses of Biomarker Endpoints

Not applicable.

10. Changes From Protocol-specified Analyses

There are no changes to the protocol-specified analyses.

11. Literature Citations / References

National Cholesterol Education Program (NCEP) Expert Panel on Detection, Evaluation, and Treatment of High Blood Cholesterol in Adults (Adult Treatment Panel III). Third Report of the National Cholesterol Education Program (NCEP) Expert Panel on Detection, Evaluation, and Treatment of High Blood Cholesterol in Adults (Adult Treatment Panel III) final report. *Circulation*. 2002;106:3143-3421.

12. Prioritization of Analyses

Not applicable.

13. Data Not Covered by This Plan

Currently there are no pre-planned analyses for the biochemical cardiovascular biomarker objective.

Protocol Number: 20170199

Date: 09 March 2019 Page 17 of 19

14. Appendices

Protocol Number: 20170199

Date: 09 March 2019 Page 18 of 19

Appendix A. Analytical Study Week Assignments

Selected endpoints will be summarized by scheduled study visits in descriptive analyses. Since the actual visits may not exactly coincide with their scheduled visit day, the actual visit day is mapped to the study visit generally by non-overlapping consecutive intervals covering the entire time continuum, with scheduled visit time being the center of each interval. The mapping intervals for all distinct schedules are summarized in the following table.

Scheduled Visit Week	Target Study Day	Vital Signs (BP, HR)	Physical Examinations	Fasting lipids, ApoA1, ApoB	Lp(a)
Week 1 (Day1)	1	<=1	<=1	<=1	<=1
Week 8	57	(1,70]	N/A	(1,70]	(1,70]
Week 12	85	> 70	> 1	> 70	> 70

Handling multiple records assigned to an analytical study week:

If there is more than one record in a study week interval, the analytical record for that specific study week will be defined as the record closest to the scheduled study day of that specific study week (7×study week). If two records are equidistant from the scheduled day, then the earlier record will be chosen. If there are multiple records on the same day, the last record will be used.

Protocol Number: 20170199

Date: 09 March 2019 Page 19 of 19

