9.1.2 Treatment Period

Visits will occur per the Schedule of Activities (Table 2-1). On-study visits may be completed within \pm 7 days. The date of the first dose of investigational product is defined as day 1 (week 1). All subsequent doses and study visits will be scheduled based on the day 1 date. Administration of protocol-required therapies is to be administered last during each visit that it is required.

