5.1 Study Time Points

Enrollment Date

The enrollment date is defined as the date collected on the electronic case report form (eCRF).

Study Day 1

For each subject, Study Day 1 is defined as the first day of IP administration in this study. If a subject never received IP, then Study Day 1 is defined as the date of enrollment.

Study Day

For each subject, and for a given study visit date, Study Day is defined as the number of days since Study Day 1:

Study Day = (study visit date – Study Day 1 date) + 1

If the date of interest is prior to the Study Day 1:

Study Day = (study visit date – Study Day 1 date), so that the day prior to Study Day 1 is study day -1.

Protocol Number: 20170199

Date: 09 March 2019 Page 8 of 19

End of Investigational Product (EOIP) Date

For each subject, the end of investigational product date is defined as the date of decision was made to end investigational product recorded on the End of Investigational Product Administration form in eCRF.

End of Study (EOS) Date

For each subject, the end of study date is the date recorded on the End of Study eCRF.

Last IP Dose Date

For each subject, the Last IP Dose Date is defined as the last day of IP administration in this study:

- If the last dose was administered non-clinic, then Last IP Dose Date is defined as the final dose date reported by the subject on the Non-Clinic Final Investigational Product Dose Date Form in eCRF.
- If the last dose was administered in-clinic, then Last IP Dose Date is the last start date captured on the Investigational Product Administration (In-clinic) form in eCRF.

Study End Date

The study end date is the last EOS date of all enrolled subjects.

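### SAP Appendix A picks among multiple records by distance from days 56 and 84, while its own table targets days 57 and 85

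*SAP*

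**What the plan says.** SAP 5.1 makes the first dose day Study Day 1 and counts forward with "Study Day = (study visit date – Study Day 1 date) + 1". The table in SAP Appendix A has a target-day column with 57 for week 8 and 85 for week 12. For fasting lipids, ApoB and Lp(a), the week-8 window is (1,70] and the week-12 window is every day after 70.

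The text around the table does two further things:

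- It describes the windows as "non-overlapping consecutive intervals covering the entire time continuum", "with scheduled visit time being the center of each interval". The sentence is worded as what is generally done.
- When several records fall in one window, it selects the one "closest to the scheduled study day of that specific study week (7×study week". It adds: "If two records are equidistant from the scheduled day, then the earlier record will be chosen".

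On timing, Protocol 9.1.2 says "On-study visits may be completed within" ±7 days. Protocol Table 2-1 schedules one lipid sample at week 8 and one at week 12 after day 1. Protocol 9.1.3 places the EOS visit of a subject who leaves the study 4 weeks (±2 days) after the last dose.

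**The concern.** The appendix gives two different scheduled days for the same visit, one in the table and one in the selection rule. The rule decides which LDL-C, ApoB or Lp(a) value becomes a subject's week-12 value, and week-12 percent change in these three is the whole set of secondary endpoints. Two programmers working from the same page could derive different records, one by following the table and the other the formula. The description of the windows also fails to match the windows in the table, so it cannot be used to settle which anchor was meant.

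**Working it through.** **1. Reproducing the targets.** With date difference + 1, the visit 7w days after the first dose falls on day 7w + 1.

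| Visit | Study Day formula (SAP 5.1) | Table (Appendix A) | Selection rule, 7×week |
|---|---|---|---|
| Week 8 | 7×8 + 1 = 57 | 57 | 56 |
| Week 12 | 7×12 + 1 = 85 | 85 | 84 |

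The table is reproduced exactly. The selection rule is one day early at both visits.

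**2. When the choice changes.** Take two records on days a < b and a target T, with ties going to the earlier record. The later record is chosen only if it is strictly nearer, that is, if a + b < 2T.

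- T = 84: b is chosen if a + b < 168.
- T = 85: b is chosen if a + b < 170.

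The two disagree only when a + b is 168 or 169. The rule then takes a, and the table's target would take b. In those pairs a lies before day 85 and b on or after it, so a is further from day 85 by (85 − a) − (b − 85) = 170 − (a + b). That is 2 days for a sum of 168 and 1 day for a sum of 169. For week 8 the same argument gives sums of 112 and 113.

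**3. How many pairs.** The ±7-day window around day 85 is days 78–92, which is 15 days and 15×14/2 = 105 pairs.

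- Sum 168: a = 78 to 83 (78/90 to 83/85), 6 pairs.
- Sum 169: a = 78 to 84 (78/91 to 84/85), 7 pairs.
- Total 13 of 105, or 12.4%.

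For week 8 (days 50–64), the sums 112 and 113 give 6 + 7 = 13 of 105 again.

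**4. Centring.** The window (1,70] covers days 2–70, with midpoint (2 + 70)/2 = 36, which is 57 − 36 = 21 days before its target. The week-12 window has no upper end and so no centre. The halfway point between the targets is (57 + 85)/2 = 71. The table cuts at 70, which is (56 + 84)/2. The practical effect of the cut is nil or nearly so: day 70 is nearer to 57 (13 days against 15), and day 71 is 14 days from both.

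**5. Which off-schedule values can enter week 12.** Visits on days 50–64 and 78–92 all land in the intended window. For subjects who leave the study, the EOS visit falls 26 to 30 days after the last dose:

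- Week-4 dose, given as late as day 29 + 7 = 36: EOS by day 66, mapped to week 8.
- Week-6 dose (apheresis subjects only), day 43: EOS on days 69–73, or 62–80 if the dose itself is ±7 days. From day 71 it is mapped to week 12, up to 14 days before target.
- Week-8 dose given as early as day 50: EOS could fall on day 76, two days short of the ±7-day window.
- Any sample after day 92, however late, is also mapped to week 12.

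**The case against.** The strongest reply is that the mismatch will hardly ever be felt. The week-12 visit is the EOS visit, so there is no second scheduled draw to compete with it, and the anchor is irrelevant for a subject with one sample per visit. In all 13 counted pairs both samples lie inside the protocol's visit window, and the one taken is at most 2 days further from target. That stands, and it limits the size of the point. It does not remove it. Protocol Appendix 2 allows additional tests at any time, the SAP saw fit to write a rule for multiple records, and that rule contradicts its own table.

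A reader might infer several stronger things that the documents do not support.

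- *That the windows break a promise of finite limits.* The SAP makes no such promise. It says the intervals cover all time, and an open-ended last window does so. An interval that must run on indefinitely cannot also be centred, so the fault lies in the centring statement, which is itself qualified.
- *That 12.4% of subjects, or of duplicate samples, are affected.* The figure is a share of equally weighted hypothetical pairs.
- *That week 1 is corrupted because 7×1 gives day 7, outside its window of day 1 or earlier.* Every candidate there is on or before day 1, so the latest day is nearest under either anchor. Lipid baseline is defined separately in SAP 5.2.
- *That an exit sample near day 29, labelled week 8, harms the efficacy endpoint.* Only week 12 is an endpoint.
- *That early-exit samples will commonly pass as week 12.* Subjects who stop drug are asked to keep attending, so the early EOS visit applies only to those leaving the study. The main route is an apheresis subject leaving after a week-6 dose, and Protocol 3.2.1 describes apheresis as not readily available in India. Such a sample is still about 4 weeks after the last dose, as the scheduled week-12 sample is.

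**Conclusion.** The contradiction is certain: 57 and 85 in the table and under SAP 5.1, against 56 and 84 in the selection rule. Its effect is small. It needs a subject with two records in one window whose days sum to 168 or 169 (112 or 113 for week 8). In those cases the rule always takes the record further from the table's target, by 1 or 2 days. If that subject's two percent changes differ by d, a mean over about 30 subjects moves by d/30. The endpoints are secondary and descriptive with no inference planned, so no error rate, sample size or primary safety result is touched.

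The centring statement is wrong for both post-baseline lipid windows. The open week-12 window is a separate and optional matter of transparency. It could admit a value from days 71–77 or after day 92 without any mark in the summary. The documents give no count of repeat samples or apheresis subjects, so the number of subjects affected cannot be estimated. These conclusions assume that visits follow the protocol's ±7 days and that any repeat central-laboratory lipid result would enter the windowing.

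**What to change.** In the multiple-record rule of SAP Appendix A, replace the bracketed 7×study week with a reference to the target study day in the table (57 for week 8, 85 for week 12). Changing the table instead would put it at odds with SAP 5.1.

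Reword the centring sentence to describe the windows actually used: they cover all time after day 1 and are split between the week-8 and week-12 targets. If the split is meant to be halfway, state it as day 71 and say which visit day 71 belongs to.

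Optionally, flag in the week-12 lipid summary any value taken outside the protocol's ±7-day window, such as a discontinuation EOS sample from day 71 on or a very late one. Flagging keeps the value in the summary. Finite windows would drop it, which is a harder choice with about 30 subjects and no imputation, and would also give up the full coverage the appendix states.

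The cost is a few words in the SAP and one derivation line before database lock, plus a footnote or listing if the flag is adopted. No data collection changes.

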Appendix B. Common Terminology Criteria for Adverse Events

Refer to the NCI Common Terminology Criteria for AEs (CTCAE) Version 4.0, published: May 29, 2009 (v4.03: June 14, 2010) for AE and lab shift grading and information. The CTCAE is available at the following link: http://evs.nci.nih.gov/ftp1/CTCAE/About.html
